**LIST OF ABBREVIATIONS AND RELEVANT DEFINITIONS**

ABR	General Assessment and Registration form (ABR form), the application form that is required for submission to the accredited Ethics Committee; in Dutch: Algemeen Beoordelings- en Registratieformulier (ABR-formulier)
AE	Adverse Event
AR	Adverse Reaction
AVL-AV	Aangepaste Versie van de Aggressie Vragenlijst
CA	Competent Authority
CCMO	Central Committee on Research Involving Human Subjects; in Dutch: Centrale Commissie Mensgebonden Onderzoek
CV	Curriculum Vitae
CVTRQ	Corrections Victoria Treatment Readiness Questionnaire
DSMB	Data Safety Monitoring Board
EU	European Union
EudraCT	European drug regulatory affairs Clinical Trials
FARE	Forensisch Ambulante Risico Evaluatie
GCP	Good Clinical Practice
GDPR	General Data Protection Regulation; in Dutch: Algemene Verordening Gegevensbescherming (AVG)
IB	Investigator's Brochure
IC	Informed Consent
IMP	Investigational Medicinal Product
IMPD	Investigational Medicinal Product Dossier
METC	Medical research ethics committee (MREC); in Dutch: medisch-ethische toetsingscommissie (METC)
RCT	Randomized Controlled Trial
RESE	Regulatory Emotional Self-efficacy scale
(S)AE	(Serious) Adverse Event
SPC	Summary of Product Characteristics; in Dutch: officiële productinformatie IB1-tekst
Sponsor	The sponsor is the party that commissions the organisation or performance of the research, for example a pharmaceutical

company, academic hospital, scientific organisation or investigator. A party that provides funding for a study but does not commission it is not regarded as the sponsor, but referred to as a subsidising party.

SUSAR	Suspected Unexpected Serious Adverse Reaction
TAU	Treatment as usual
TWEETS	TWente Engagement with Ehealth and Technologies Scale
UAVG	Dutch Act on Implementation of the General Data Protection Regulation; in Dutch: Uitvoeringswet AVG
WMO	Medical Research Involving Human Subjects Act; in Dutch: Wet Medisch-wetenschappelijk Onderzoek met Mensen

## SUMMARY

**Rationale:** While internet-based interventions have been used for over ten years in Dutch forensic psychiatric outpatient care, no thorough evaluation study has been conducted yet. Studies on internet-based interventions in other mental healthcare sectors show promising results: they can increase the quality and efficiency of care. However, it is not clear if, why and for whom these interventions work in forensic mental healthcare. It is especially important to study whether these interventions are of added value for this complex patient population, known for its low treatment motivation, co-morbidity and low literacy levels.

**Objective:** The primary objective of this study is to investigate whether the addition of the internet-based intervention 'Aggression' to forensic psychiatric outpatient treatment as usual (TAU) results in better treatment outcomes in terms of self-reported regulatory emotional self-efficacy, treatment readiness, and aggression. Additionally, it is investigated whether the experimental group requires fewer treatment sessions and improves more on dynamic risk factors. Furthermore, to gain more insight into for whom these interventions work, it is investigated whether engagement with the internet-based intervention predicts adherence and effectiveness. Finally, this study aims to explore reasons for the (in)effectiveness of the intervention according to patients and therapists.

**Study design:** To investigate if the use of internet-based interventions is of added value for treatment of forensic psychiatric outpatients, a multicenter, non-blinded, parallel groups, randomized controlled trial design is used. Patients fill out three short self-report questionnaires four times: at baseline, mid-treatment (+6 weeks), post-treatment (+14 weeks) and at follow-up (+26 weeks). Semi-structured interviews with a randomly selected sample of 20 patients from the experimental condition and with all participating therapists are conducted to explain the results of the RCT.

**Study population:** The target group of this study consists of forensic psychiatric outpatients, treated in four Dutch organizations for aggression regulation problems.

**Intervention (if applicable):** This study investigates the existing internet-based intervention Aggression, which was introduced in forensic mental healthcare over ten years ago. However, as is the case with other internet-based interventions, uptake in practice remains relatively low. 'Aggression' is used as an addition to treatment as usual, and thus does not replace any part of treatment in this study. The intervention is earlier developed by the CE-certified company Minddistrict. The last couple of months the intervention has been cosmetically adjusted in close cooperation with therapists, patients and other stakeholders so that it fits the current design and lay-out of Minddistrict. The goals of this intervention are to (1) increasing the motivation to change, (2) acquiring skills for dealing with conflict, and (3) breaking the cycle of aggression by providing knowledge on situational, emotional, cognitive

and physical triggers. It contains ten lessons, each containing written texts, videos and audio files, and short written assignments on which the therapist can give feedback.

**Main study parameters/endpoints:** All participants fill out three validated, short self-report questionnaires on self-efficacy, treatment readiness and aggression at four points during the study. Participants in the experimental conditions also fill out an engagement questionnaire during the use of the intervention. Dynamic risk factors are assessed via a risk assessment instrument that is already used as a standard part of treatment according to Dutch guidelines and the number of treatment sessions are retrieved from existing systems. The patient and therapist perspective is taken into account by means of semi-structured interviews.

**Nature and extent of the burden and risks associated with participation, benefit and group relatedness:** Since participants only have to fill out short questionnaires and are compensated for their time, participating in this study is not viewed as a major burden. Furthermore, the interventions of Minddistrict have been used for over ten years in mental healthcare, during which no risks or adverse events have been observed. Because –not all forensic psychiatric patients receive internet-based interventions as part of their standard care and because these interventions are not yet evaluated and are thus not evidence-based, participants in the control condition are not deprived of effective treatment. During the entire study, experienced therapists monitor the patient's progress. Finally, multiple precautions are taken to ensure that patients are aware that the decision to participate does not have any effect on their treatment progress. Consequently, the burdens and risks associated with this study are low or even non-existent.

## 1. INTRODUCTION AND RATIONALE

Forensic mental healthcare is a complex branch of care which takes place at the intersection of psychiatry and law [1-3]. In forensic psychiatry, patients that show aggressive or sexual delinquent behaviour and have one or more concurrent psychiatric disorders are treated. Both in- and outpatients are often treated mandatory, as part of a sentence, which can result in overall low treatment motivation [4, 5]. Additionally, a relatively large share of the forensic psychiatric patient population has low cognitive and adaptive skills and often suffer from multiple psychiatric disorders [6-9]. These factors highlight the complexity of treating forensic psychiatric patients. While treatment, guided by for example the Risk-Need-Responsivity model, has resulted in lower recidivism rates, these numbers are not as low as desirable [10-12]. Furthermore, when looking at the use of cognitive behavioural therapy (CBT) in this group, effectiveness rates for CBT for aggression are lower than those for treatment of for example anxiety [13, 14]. Besides these complicating factors, there also is a shortage of healthcare providers, while there also is an increase in forensic psychiatric patients that require treatment [15]. In general, it becomes clear that there is room for improvement in treatment for these vulnerable patients.

In clinical practice, eHealth interventions are used to address the aforementioned challenges. The past ten years, Dutch forensic psychiatric organizations have especially invested in internet-based interventions, with the expectation that these interventions can increase efficiency and quality of forensic mental healthcare [16, 17]. Internet-based interventions are often based on evidence-based treatment models such as CBT and present the user with knowledge and skills via multiple lessons with e.g. multi-media such as videos, written assignments and short texts [18]. While users can work on these digital interventions independently, the therapist can provide written feedback on the assignments. Over the past years, different types of these interventions have been introduced and used in Dutch forensic mental healthcare [19, 20]. Existing internet-based interventions are focused on e.g. aggression, offense scripts and prevention plans, addiction, or violence in relationships [21]. Even though these digital interventions have been integrated in forensic mental healthcare for almost ten years, their effectiveness in Dutch outpatients has never been studied. In line with this, a scoping review on technology in treatment of offenders has shown that these interventions are also hardly evaluated in other countries [16]. The very few evaluation studies that were conducted focused on inpatients in for example prisons or clinics, while a large share of the patient population is treated at outpatient clinics. Consequently, this very complex and vulnerable target group is underrepresented in intervention research.

Even though there is an obvious and urgent need for more research on the effectiveness of these interventions in forensic mental healthcare, existing evidence suggests that this form of eHealth might have advantages for forensic patients. In the

aforementioned review, 13 studies evaluated effectiveness of internet-based interventions in experimental designs [16]. Of these studies, 10 showed that these interventions were at least as effective as standard care or more effective than a waiting list condition, while 3 studies found no evidence for effectiveness. This means that the most of the few existing studies have shown the effectiveness of these interventions in treatment of offenders. In addition to that, systematic reviews on digital interventions in mental healthcare in general show comparable findings. For example, if used well, internet-based interventions focused on a broad range psychiatric and somatic disorders result in comparable outcomes as face-to-face interventions [22, 23]. Additionally, qualitative research with therapists and patients has identified multiple experienced benefits for patients. Examples are receiving better and more tailored information about the problematic behaviour via multimedia such as videos or assignments, attributing change to one's own work on the intervention as opposed to just the therapist, and acquiring more tools on dealing with aggression by means of tips and assignments [19, 21]. Consequently, while earlier research suggests that these interventions might work for forensic mental healthcare as well [16], there is a need to study them in Dutch forensic outpatient care, since earlier findings cannot simply be generalized to this complex and highly specialized branch of care. Additionally, internet-based interventions are often studied in a fully online way and separately from treatment, while in practice, they are used in a blended way, i.e. integrated in treatment [24].

While no robust effectiveness studies have been conducted on the use of internet-based interventions in forensic outpatient care, earlier research has provided several useful insights and recommendations. First, a straightforward recommendation is to study the effectiveness of internet-based interventions in clinical practice to gain insight into whether they work [17, 19]. However, merely gaining insight in effectiveness does not fully answer all questions that arise from research and practice. Consequently, a second recommendation is related to the use of these interventions. A recent study on implementation of these internet-based interventions in forensic outpatient care has shown that adherence to them is low: most patients don't complete all lessons of a intervention and a large share drops out after one session [21]. While an important reason for this is that therapists forget to introduce these modules to patients and do not integrate and discuss them in treatment sessions, explanations for non-adherence might also be found in patient characteristics. This highlights the importance of research that determines if and how we can predict if a patient drops out of the intervention. A third recommendation is related to the 'what works for whom' question. Therapists indicate that internet-based interventions do not seem to fit the entire forensic psychiatric population, but can be of added value for some patients. However, this is merely based on clinical experiences and subjective estimations: there has not been research on this topic yet. In other words: up until now, there is no clear explanation of why an

intervention might work for one, but not for another patient. Socio-demographics do not provide satisfactory answers to questions regarding what works for whom. Research shows that engagement might be a novel and useful factor that might provide insight into why interventions work for specific patients [25, 26]. Engagement refers to the extent to which someone is involved or occupied with something, and is often related to a positive outcome. In relation to eHealth, it can serve as a predictor for adherence and engagement [25, 26]. However, the role of engagement in internet-based interventions has not been studied in forensic mental healthcare. Fourth, even if internet-based interventions are shown to be effective, it has proven to be very challenging to implement them in clinical practice. Research on the implementation of these interventions in forensic mental healthcare has indeed shown that implementation is suboptimal [21]. Qualitative, in-depth research into experiences and needs of not only patients, but also therapists is required to gain more insight into implementation barriers and potential activities.

It is clear that there is a pressing need for research into if, why and for whom internet-based interventions work. Qualitative research has highlighted several potential benefits of internet-based interventions that require further research [19, 21]. These outcomes were mostly related to aggression regulation, since this is an important and large part of outpatient treatment. In general, therapists did see multiple advantages, but indicated that they did not expect any major improvements due to these interventions: they were mostly expected to slightly bolster the effectiveness of existing treatment, mostly by providing patients with more tools to work on their treatment independently. Because of this, changes might be attributed to the patient's own effort as opposed to that of the therapist, which could benefit **self-efficacy** towards behaviour change. Additionally, internet-based interventions offer multiple ways of acquiring knowledge and skills that are tailored to the target group, such as multi-media, written assignments and peer-stories. This is done to accommodate different types of learning that better fit the patient than face-to-face treatment sessions and can thus also increase the patient's confidence in regulating their aggression. Furthermore, therapists also expected that these intervention can positively affect **treatment readiness** of patients because they can support the patient in gaining insight into their problems and defining their own goals. Being responsible for their own treatment by working on an internet-based intervention individually, and gaining more insight into their own behaviour, might influence their sense of ownership and motivation to work on their treatment. Therapists, patients and researchers expect that this potential increase in self-efficacy and treatment readiness could facilitate actual behaviour change: **aggression** might decrease due to the independence, knowledge, insights and skills that are acquired by means of these interventions [17]. This can result in decreased risk for recidivism, reflected in an improved score on **risk assessment instruments**. Finally, it is also expect that, if used well, these

interventions might result in more **efficient treatment** because part of face-to-face treatment can be replaced by the internet-based intervention [21, 27]. However, for all of these expectations goes that they are based on qualitative research.

Besides potential advantages of internet-based interventions, there are also critical views on these interventions. These are partly related to an expected misfit between the mostly language-driven interventions and relatively low educated and generally unmotivated patient population [21, 27, 28]. In general, therapists identify a broad range of improvements of these interventions, related to their content, the design, and the integration in clinical practice [21]. Robust evaluation research is required to investigate whether these internet-based interventions are of added value for forensic outpatient care and to answer questions about adherence, engagement, effectiveness and implementation barriers

The present study aims to fill the current gap in research on internet-based interventions in forensic psychiatric outpatient care. By evaluating an existing intervention that is already used in practice by means of a robust randomized controlled trial design, this study will have high clinical relevance and impact on practice. We will study the existing, evidence-based internet-based intervention 'Aggression', which contains 10 lessons and thus takes 10 weeks. Furthermore, our quantitative and qualitative results will provide valuable points of improvements for the content and design of the intervention and for its integration in forensic outpatient care. This type of research is especially relevant for forensic psychiatric patients: a vulnerable yet underrepresented target group that requires better, more fitting and evidence-based treatment to increase their quality of live, prevent recidivism and thus also protect society.

## 2. OBJECTIVES

### ***Primary objective***

The primary objective of this study is to investigate whether the addition of the internet-based intervention 'Aggression' to forensic psychiatric outpatient treatment as usual (TAU) results in better treatment outcomes on the short and long term than patients that only receive TAU.

### ***Secondary objectives***

The secondary objectives are:

1. To determine if there is more improvement in improvement regulatory emotional self-efficacy, treatment readiness, and aggression in the experimental than control group during, directly after completing, and three months after completing the internet-based intervention 'Aggression'.
2. To determine if there is more improvement on dynamic risk in the experimental than the control group after completing the internet-based intervention 'Aggression'.
3. To determine if the number of face-to-face treatment contacts over a period of 37 weeks is lower in the experimental than the control group.
4. To determine if the level of engagement with the intervention measured at the beginning, halfway and at the end of the internet-based intervention Aggression, and the adherence to the intervention, is a predictor for effectiveness.
5. To map experiences with the internet-based intervention Aggression of forensic psychiatric patients that followed (part of) the intervention.
6. To map experiences with the internet-based intervention Aggression of therapists that used the intervention in at least five patients.

### 3. STUDY DESIGN

#### 3.1 Study design

Even though internet-based interventions are being used on a large scale and for a fairly long time, there have not been any robust evaluation studies in forensic mental healthcare. There have been small non-scientific pilots in single organizations and several mostly qualitative studies on their implementation [19-21]. A randomized controlled trial (RCT) in which the intervention as an addition to treatment as usual (TAU) compared to a control group that only receives TAU is a suitable research method to evaluate whether the addition of these types of internet-based interventions adds to the effectiveness of treatment [29]. RCTs are viewed as a suitable research method - even the golden standard - when studying effectiveness of interventions. In order to also gain insight into why this might be the case and what points of improvements are, qualitative data will be collected as well [30]. In this study, interviews with patients and therapists are conducted after data-analysis of the RCT to ask them about reasons for the (in)effectiveness of the internet-based intervention and implementation conditions. In this way, the perspectives of patients and therapists – both essential for successful use of internet-based interventions – are integrated in the study. Furthermore, a multicenter approach is used to increase the feasibility of the study and to ensure that findings are not just based on one outpatient clinic and thus are more generalizable.

Consequently, to investigate if the use of the internet-based interventions Aggression is of added value for in-person treatment of forensic psychiatric outpatients, a multicenter, non-blinded, parallel groups randomized controlled trial design is used.

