#### 3.2 Setting of the study

This multicenter study will take place in four Dutch forensic psychiatric organizations that offer forensic psychiatric outpatient care: Stichting Transfore, Kairos, de Woenselse Poort and GGZ Noord-Holland Noord.

This study is initiated and will be coordinated by Stichting Transfore, an organization that has the goal to be frontrunner in developing and providing eHealth in forensic care. Transfore has participated actively on the development of multiple Minddistrict modules and other eHealth interventions. Additionally, Transfore has been conducting multiple implementation- and evaluation research, to – among other things – internet-based interventions. GGZ Noord-Holland-Noord started experimenting with internet therapy in 2001. Nowadays, multiple applications of eHealth are integrated in treatment methods. Together with other GGZ-providers, GGZ Noord-Holland-Noord developed multiple (forensic) modules for the Minddistrict platform. De Woenselse Poort is part of GGzE and is also a frontrunner on

innovation in (forensic) mental healthcare. Many of their projects are focused on eHealth: Minddistrict, mobile apps and virtual reality. Kairos is part of Pompestichting which has been inducting research on multiple areas for many years. Their main focus lies on technology and innovation, and other ways to improve treatment methods.

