Patients will start with the Aggression module after approximately 12 weeks: this might exceed to a maximum of 14 weeks, if the patient for example is not able to start yet or misses several treatment sessions – which happens often in forensic mental healthcare. Participants are assessed four times throughout the study. They are first assessed at

[figure not shown]

baseline (T0), i.e. in week 12. A mid-treatment assessment (T1) is conducted when participants are supposed to be halfway throughout the internet-based intervention, i.e. 6 weeks after baseline, so in week 17. After completing the intervention, post-treatment assessment will be conducted. If participants complete a lesson per week, the intervention should be finished after 11 weeks. However, in practice, this often is not the case, for example because the patient misses treatment sessions or other psychosocial crises can arise that have priority. Consequently, post-treatment assessment will take place 14 weeks after baseline, i.e. in week 25. Finally, a follow-up assessment will be conducted. This assessment will take place 3 months after T2, so during week 37 of the entire study.

At all assessment points, patients will fill out three self-report questionnaires via Qualtrics: Regulatory Emotional Self-efficacy (RESE) scale [31], the Corrections Victoria Treatment Readiness Questionnaire (CVTRQ): a validated self-reported questionnaire [32], and the Dutch version of the Aggression Questionnaire (AVL-AV) [33, 34]. Participants in the experimental condition also fill out the the TWente Engagement with Ehealth and Technologies Scale (TWEETS) [35] at the beginning, halfway and at the end of the internet-based intervention Aggression. Furthermore, the scores of the risk assessment instrument 'Forensisch Ambulante Risico Evaluatie (FARE) [36] - which is part of standard procedures – will be used to assess change in dynamic risk factors in all participants .

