## **8.2 Randomisation, blinding and treatment allocation**

Because blinding is impossible due to the use of the internet-based intervention in treatment, this study is a non-blinded RCT. After a participant is screened and has given informed consent, they will be randomized by the principal investigator. The randomization will be supported by an online tool (<https://sealedenvelope.com/>). Participants are not randomized per participating organization or clinic because there are major differences in the number of patients treated by these clinics. Instead, once a patient is included, they receive a participant number, which will be aligned with a random sequence of treatment allocations, i.e. participants are either allocated to the intervention or control group. The first participant included in the study is allocated according to the first treatment allocation on the list, the second participant according to the second allocation, and so forth.

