Participating therapists are informed of the group the patient is allocated to and will explain this to the patient. If a patient is randomized into the control condition, the therapist is instructed to provide treatment as usual, and can be contacted by the researcher in case a patient did not fill out questionnaires at T0, T1, T2 or T3. If a patient is randomized into the experimental group, the therapist is asked to start with the intervention 'Aggression'. Specifically, the therapist will shortly explain the goal, content and nature of the internet-based intervention and explain to the patient that they will receive one lesson per week for the next 10 weeks. Additionally, the therapist will provide written feedback on the assignments of the patients. All participating therapists are trained in the use of these types of interventions and thus know how to provide feedback. To increase the feasibility of this study and reach the intended number of participants, therapists will receive additional support from researchers to remind them to introduce the intervention. The main reason for this is that implementation research on these types of internet-based interventions in Dutch forensic outpatient care has shown that, even though therapists have the intention to use the intervention, they often forget to introduce the intervention. Additionally, if they introduced the intervention, therapists often do not mention it in their treatment sessions. Consequently, participating therapists will be regularly reminded to introduce and keep on discussing the internet-based interventions with the patients in the experimental condition.

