**8.5 Withdrawal of individual subjects**

Subjects can leave the study at any time for any reason if they wish to do so without any consequences. The investigator can decide to withdraw a subject from the study for urgent medical reasons. Patients can also be withdrawn in case of a severe psychiatric crisis and/or admission to a (forensic) psychiatric hospital, other type of inpatient clinic, or prison.

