## 12. ADMINISTRATIVE ASPECTS, MONITORING AND PUBLICATION

### 12.1 Handling and storage of data and documents

All data generated during screening and the study itself will be handled confidentially and anonymously in accordance with the EU General Data Protection Regulation and the Dutch Act on Implementation of the General Data Protection Regulation. Personal data will be coded with an individual ID-code, which is not relatable to the participant. A list will be created, which contains the ID-codes, stored on a separate drive on a computer and maintained by the principal investigator at her office in the Department of Psychology, Health and Technology of the University of Twente. Both the office, the drive, the computer, and the file containing the ID-codes will be locked with a key and password. All collected data will be stored in a file containing only the identification code to be able to match the data of the same person across different measurement points. These data will be stored and collected on a shared drive that is password protected and only accessible to the researchers. The key of the research data will be stored at the local centra that are participating.

During the research period the coded research data will be stored at the University of Twente. After the research is completed, the data will be stored in a long time storage at Data Archiving and Networked Services (DANS) by the Royal Dutch Academy of Sciences (KNAW) after which the ID codes key file ownership and maintenance is transferred to the secretary of the department of Psychology, Health and Technology of the University of Twente. After 15 years the data will be deleted.

Participants who want to be informed about their personal data or who want their data deleted can send a request to the principal investigator. For this, no reason is needed, since participants always have the right to be informed about their personal data. After the personal data is deleted, informing participants about their personal data is no longer possible.

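### The reason given for no blinding covers only patients and therapists, and no masked analysis is planned although choices that decide the T3 verdict are still open

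*Combined protocol and SAP*

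**What the plan says.** Section 3.1 applies one label to the whole trial: "a multicenter, non-blinded, parallel groups randomized controlled trial design is used". Section 8.2 gives the reason: "Because blinding is impossible due to the use of the internet-based intervention in treatment, this study is a non-blinded RCT". The same section says that after consent "they will be randomized by the principal investigator" (Section 8.3, Step 5, says the researcher), and that "Participating therapists are informed of the group the patient is allocated to and will explain this to the patient". It also aligns the participant number with the random allocation sequence.

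The three main outcomes are self-reported: "patients will fill out three self-report questionnaires via Qualtrics" (Section 3.3).

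Section 10.1 specifies intention to treat, a mixed model with time, group and their interaction as fixed effects and participant as a random effect, and a set of effectiveness scenarios. On removal after randomisation, Section 8.5 says "Patients can also be withdrawn in case of a severe psychiatric crisis and/or admission". Section 8.7 excludes everyone who leaves treatment entirely. Section 8.8 would, after early termination, analyse those who completed the study.

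Section 12.1 stores data under an ID code and does not say whether the arm is masked in that file.

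**The concern.** Use of the module in treatment makes it impossible to hide the arm from the patient and the therapist. It does not prevent a file with neutral arm codes from being cleaned and modelled. Labelling the whole trial non-blinded passes over that possibility and gives no reason for doing so.

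This matters because the plan leaves real decisions to be made later, and each can bear on whether the module is called effective. If they are settled by people who can see which arm gains from each option, the nominal 5% level no longer describes the procedure. The main outcomes are self-reports by patients who know their arm, so the analysis is one of the few stages at which knowledge of allocation can still be removed.

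**Working it through.** **1. The plan's own figure.** Section 4.4 uses d = 0.5, two-sided alpha 0.05, power 0.80 and an independent t-test. The normal approximation is n = 2(1.96 + 0.84)²/0.5² ≈ 62.8, so 63 per arm. The noncentral t gives 63.77, so 64 per arm and 128 in total, with power 0.801. The stated 64 reproduces. Masking the analysis changes none of these inputs.

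**2. Who the stated reason reaches.**

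| Role | Does the reason in 8.2 apply? | Is masking planned? |
|---|---|---|
| Patient, therapist | Yes | No, and not feasible |
| Researcher who randomises | Knows the arm by role | No |
| Person who fixes the analysis set and runs the model | No | Not mentioned |

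**3. What is still open.**

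- *Deciding test.* Section 10.1 names the interaction and also LSD post-hoc t-tests with Bonferroni correction. LSD is unadjusted and Bonferroni is adjusted. The number of comparisons is not given, nor is the test that yields the T3 verdict.
- *Covariance structure.* Not specified.
- *Effectiveness rule.* Section 8.1 calls the intervention effective if all three outcomes change at T3. The scenarios in Section 10.1 call it effective with one or two at T3.
- *Analysis set.* Intention to treat (10.1) conflicts with exclusion of those who leave treatment (8.7) and with completers after early termination (8.8).

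**4. Illustration for the analysis set.** The documents give no figures for this, so the inputs are assumptions: 64 per arm, standard-normal scores oriented so that higher is better, no true effect, pooled t-test, and k patients removed from the experimental arm only. The result is the chance of p < 0.05 in favour of that arm; the nominal value is 2.5%.

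| k removed | Lowest T3 scores removed | Lowest on an earlier score, r = 0.5 with T3 | Same, r = 0.3 |
|---|---|---|---|
| 2 | 6.5% | 3.8% | 3.2% |
| 3 | 9.2% | 4.7% | 3.6% |
| 4 | 12.1% | 5.6% | 4.0% |
| 5 | 15.6% | 6.6% | 4.5% |

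The first results column corresponds to mean shifts of 0.071, 0.099, 0.126 and 0.154 SD. It requires whoever removes patients to know their T3 results, so it is a worst case. The other two columns are closer to withdrawals that precede T3, but they still assume that every removal takes a lowest scorer from one arm.

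A milder version takes 154/2 = 77 per arm and removes k patients whose scores average m SD below the mean. The shift is k·m/(77 − k). For k = 2, m = 0.5 it is 1/75 = 0.013 SD; for k = 6, m = 1.0 it is 6/71 = 0.085 SD. Total two-sided type I error is then 5.1% to 8.1%, against 5%.

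**5. Illustration for the choice of test.** Taking the smallest p-value among a raw T3 t-test, a change-score test, ANCOVA, and ANCOVA without outliers (64 per arm, no effect, baseline correlation 0.3 to 0.7) gives total type I error of about 10–11%. These four are not the plan's analyses. They indicate only what an open choice of test could do.

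**The case against.** The strongest reply is that little is left to an analyst's discretion. The main outcomes are fixed-item questionnaires, so scoring offers almost no room. The FARE is administered by the treating therapist, who knows the arm, and masking an analyst does not change that. The model class, intention to treat and the effectiveness scenarios are written down. Loose wording is cured by specifying it, not by masking. Withdrawals under Section 8.5 and exclusions under 8.7 happen during follow-up, so a masked file could arrive already thinned.

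Most of this stands as a limit on the point. Scoring is not a material exposure. The conflict between 8.7 and intention to treat needs its own repair. Masking alone does not help unless randomised patients' data are kept in the file. What the reply does not answer is that the named model leaves the deciding test, the covariance structure, the effectiveness rule and the analysis set unsettled. Masking protects those decisions for as long as they stay open.

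Two stronger readings are tempting. A reader might infer that exclusions and test choices are in fact made with arm labels visible. The documents do not say so: this would rest on the non-blinded label and on silence, and the text of Section 12.2 (Monitoring and Quality Assurance) was not available to this review. A reader might also infer that the coordinating organisation is judging its own product, because "Transfore has participated actively on the development of multiple Minddistrict modules and other eHealth interventions". Section 3.2 does not name the Aggression module among these, the Summary attributes its development to Minddistrict, and Section 12.1 keeps the coded data at the university.

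**Conclusion.** The point holds in a limited form. The justification in Section 8.2 does not extend to the analysis, no masked analysis is visible in the plan, and decisions that determine the verdict could be settled after results by arm are known. It shows a missing safeguard, not that any such decision has been or will be made.

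The size is illustrative and rests wholly on assumed removals: about 3–7% favourable false positives per outcome when removal follows an earlier score correlated 0.3 to 0.5 with T3, and 6.5–16% in the worst case, against 2.5%. The mildest assumptions give almost no inflation. Larger biases remain whatever is done here: self-report by patients who know their arm, the therapist-rated FARE, and questionnaires completed together with a researcher (Section 8.3, Step 4, with the procedure repeated at later assessments). Severity is minor to moderate.

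**What to change.** - **Wording.** In Sections 8.2 and 10.1, and in the design label in 3.1, state that the trial is not blinded for patients, therapists and the researchers who randomise, and that the between-group analyses for objectives 1 to 3 are run on masked arm codes.
- **IDs and key.** Use new analysis IDs unrelated to the allocation sequence, because Section 8.2 ties participant numbers to it. An existing team member who does not run the analysis holds the arm-code key. The key in Section 12.1 ("The key of the research data will be stored at the local centra that are participating") links IDs to persons and does not serve this purpose.
- **Staged release.** Withhold TWEETS, lesson and log data, which would reveal the experimental arm, until the masked analysis is recorded. Run the completed-lessons moderator analysis (Section 4.4) and objective 4 after unmasking.
- **Dated decisions.** Before unmasking, record the analysis set, the covariance structure, the test that decides at T3 with its multiplicity correction, and one effectiveness rule for both 8.1 and 10.1. Preferably do this before the two codes are compared at all, since masking hides the direction of a difference but not its size.
- **Complete file.** Keep the available data of all randomised patients, so that withdrawals and exclusions under 8.5 and 8.7 do not thin the file beforehand. Reconcile 8.7 and 8.8 with intention to treat. This concerns data retention only and takes no position on when a patient should be withdrawn.

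The cost is a short delay before the engagement analyses and some data-management work. Sample size, visits and patient procedures do not change.
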